Study Description	This is a single-arm, 2-stage, phase II study of the safety and efficacy of daratumumab in combination with azacitidine and dexamethasone in relapsed/refractory multiple myeloma (RRMM) patients who have previously been exposed to daratumumab. Based on pre-clinical data we hypothesize that azacitidine, by upregulating the expression of CD38, can potentially increase the antibody-dependent cell-mediated cytotoxicity and efficacy of daratumumab on multiple myeloma cells and help reverse daratumumab resistance. This study aims to assess the efficacy and safety of daratumumab and azacitidine in relapsed refractory multiple myeloma.
Phase of Study	Phase 2
Investigational Products	Daratumumab and Azacitidine
Study population	Patients \geq 18 years of age with relapsed or refractory multiple myeloma (RRMM) who have progressed on \geq 2 lines of prior therapy, including an immunomodulatory drugs (IMiD) and proteasome inhibitor, and have previously been treated with daratumumab, with most recent daratumumab treatment being at least 6 months prior to enrollment to allow for CD38 normalization.
Primary Objective	
 To evaluate the efficacy, as determined by the overall response rate (ORR) of daratumumab in combination with azacitidine and dexamethasone in RRMM patients who have previously been exposed to daratumumab
Secondary Objectives	
 To evaluate duration of response per IMWG response criteria. To assess the safety and toxicity of azacitidine in combination with daratumumab and dexamethasone To assess the 1-year OS and PFS of daratumumab in combination with azacitidine and dexamethasone To evaluate the change in CD38 expression on plasma cells induced by azacitidine in patients with RRMM and correlate this change with depth and duration of response

Sample Size	
Simon's minimax two-stage design will be used.
 
The overall study (including the safety lead-in) plans to enroll 23 patients.
 
Safety Lead In: We expect to enroll 6 patients overall in the safety lead-in.
 
Stage 1: We expect to enroll a total of 13 patients during Stage 1 (including the 6 patients enrolled in the safety lead-in). Depending on the clinical response in Stage 1, Stage 2 will commence.
 
Stage 2: If there is ≥ 2 responses in 13 patients the study will enroll an additional 10 patients.
 
If there is ≤ 1 response in 13 patients the study will be stopped.

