
While daratumumab is well tolerated and has high efficacy, not all patients respond, and many patients eventually develop progressive disease and resistance to daratumumab. A retrospective study showed that these patients have poor prognosis with a median overall survival of 5.3 months and a post-daratumumab regimen overall response rate of 34% with limited treatment options.¹⁶ Another retrospective study analyzing outcomes of 275 multiple myeloma patients at 14 academic centers with disease refractory to CD38 monoclonal antibodies (MoABs), either daratumumab or isatuximab, found that this patient population had a median overall survival (OS) of 8.6 months, ranging from 11.2 months for patients not simultaneously refractory to an immunomodulatory (IMiD) agent and a proteasome inhibitor to 5.6 months for penta-refractory patients who are

[figure not shown]
refractory to CD38 MoABs, 2 proteasome inhibitors, and 2 IMiDs.¹⁷ These studies highlight that heavily pre-treated MM patients who are resistant to daratumumab have overall poor prognosis. Thus, research has focused on understanding markers and predictors of daratumumab response and mechanisms of daratumumab resistance, which will prove to be even more important as daratumumab is being moved to frontline therapy.

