3.1 Characteristics

This is a single-arm, open label, 2-stage phase II study of the safety and efficacy of daratumumab in combination with azacitidine and dexamethasone in RRMM patients who have previously been treated with daratumumab with a safety lead-in cohort. Screening data will be reviewed to determine subject eligibility. Subjects who meet all inclusion criteria and none of the exclusion criteria will be entered into the study.

Patients will need a washout period of at least 6 months from their most recent exposure to daratumumab prior to first dose of daratumumab on the trial. This 6 month washout period will allow for CD38 normalization⁵⁶, and hence will enable the measurement of the change in CD38 expression on plasma cells secondary to azacitidine (secondary endpoint correlative study for this trial) and eliminate the confounding factor of daratumumab's effect on CD38 expression. Patients will receive azacitidine at the standard 75 mg/m² dose 5 days consecutively every 4 weeks starting day -7 to day -3 of Cycle 1 and then Day 22-26 of Cycle 1-3, and subsequently Day 1-5 of Cycle 5 and thereafter, with dose modifications for toxicities as outlined in [Section 5.5](#). Daratumumab will be administered at the standard dose of 1800 mg subcutaneously, with first dose administered on day 1. Daratumumab will be dosed in standard fashion: weekly for 8 doses (induction phase), every two weeks for 8 doses (consolidation phase), and then every 4 weeks thereafter (maintenance phase). There will be no dose modifications for daratumumab. Dexamethasone at a dose of 40 mg PO (or IV if PO is not available) will be given weekly for Cycle 1 and 2. This dose may be reduced or stopped after Cycle 2 on non-daratumumab administration weeks and as a pre-medication on daratumumab administration weeks. Further dose reduction is permitted based on dose modification criteria outlined in [Section 5.5](#). Bone marrow biopsies will be done within 14 days of Cycle 1 day -7 (first azacitidine dose) and on Cycle 1 day 1 prior to first daratumumab administration (or after completion of first 5 days of azacitidine and prior to first daratumumab administration), for correlative studies. Please see [Section 5](#) for more details on dosing of study treatment and [Section 6](#) for more details regarding correlative studies.

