3.2 Eligibility Criteria

Inclusion Criteria

1. Age ≥ 18 years
2. Patients must have a known diagnosis of multiple myeloma with evidence of measurable disease, AND have evidence of disease progression based on IMWG criteria⁵⁵.
 - o Serum M-protein ≥ 0.5 g/dL, or urine M-protein ≥ 200 mg/24 hours. OR
 - o In the absence of measurable M-protein, Serum immunoglobulin free light chain ≥ 10 mg/dL, and abnormal serum immunoglobulin kappa lambda free light chain ratio.
3. Relapsed from or refractory to 2 or more different prior therapies, including immunomodulatory drugs (IMiDs; eg, thalidomide, lenalidomide) and proteasome inhibitors, chemotherapy-based regimens, monoclonal antibodies, or autologous stem cell transplantation (ASCT).
 - o Relapse is defined as progression of disease after an initial response (MR or better) to previous treatment, more than 60 days after cessation of treatment
 - o Refractory disease is defined as $<25\%$ reduction in M-protein or progression of disease during treatment or within 60 days after cessation of treatment
4. Prior exposure to daratumumab, with most recent dose being at least 6 months prior to trial enrollment
5. ECOG performance status <2 (Karnofsky $>60\%$ (see Appendix 1)
6. Demonstrates adequate organ function as defined below within 7 days of first dose of drug:

Adequate bone marrow function:

absolute neutrophil count	$\geq 1,500/\text{mcL}$
platelets	$\geq 75,000/\text{mcL}$

Adequate hepatic function:

total bilirubin	within normal institutional limits, unless elevated due to Gilbert's syndrome and direct bilirubin is within normal limits
AST(SGOT)	$\leq 3 \times$ institutional upper limit of normal
ALT(SGPT)	$\leq 3 \times$ institutional upper limit of normal

Adequate renal function:

creatinine	$\leq 1.5 \times$ within institutional upper limit of normal
------------	--

OR

creatinine clearance

GFR \geq 60 mL/min/1.73 m², calculated using the Cockcroft-Gault equation, unless data exists supporting safe use at lower kidney function values, no lower than 30 mL/min/1.73 m²

7. Life expectancy of at least 3 months.
8. Women of childbearing potential must have at least one negative highly sensitive serum (β eta-human chorionic gonadotropin [β eta-hCG]) during screening, within one week prior to the first dose of any component of study treatment
9. Before enrollment, a woman must be either:
 - a. Not of childbearing potential defined as:
 - Postmenopausal:

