- 12. During the study (including during dose interruptions), and for 4 weeks following discontinuation of azacitidine, and for 3 months after the last daratumumab dose, in addition to the user independent highly effective method of contraception (even if he has undergone a successful vasectomy), a man
 - Who is sexually active with a woman of childbearing potential must agree to use a barrier method of contraception (ie, latex or synthetic condom with spermicidal foam/gel/film/cream/suppository)
 - Who is sexually active with a woman who is pregnant must use a latex or synthetic condom.
 - Must agree not to donate sperm
- 13. Willing and able to adhere to the prohibitions and restrictions specified in this protocol and referenced in the ICF.
- 14. Must sign an ICF (or their legally acceptable representative must sign) indicating that he or she understands the purpose of, and procedures required for, the study and is willing to participate in the study.

Any potential subject who meets any of the following criteria will be excluded from participating in the study:

Exclusion Criteria

1. Diagnosed or treated for malignancy (either solid tumor or hematologic) other than multiple myeloma, except:
 - Malignancy treated with curative intent and with no known active disease at enrollment.
 - Adequately treated non-melanoma skin cancer, lentigo maligna or in situ malignancies (including but not limited to, cervical, breast) with no evidence of disease.
2. Received daratumumab therapy less than 6 months prior to trial enrollment
3. Primary refractory to prior daratumumab
4. Subject is:
 - a. seropositive for human immunodeficiency virus (HIV)
 - b. seropositive for hepatitis B (defined by a positive test for hepatitis B surface antigen [HBsAg]). Subjects with resolved infection (ie, subjects who are HBsAg negative but positive for antibodies to hepatitis B core antigen [anti-HBc] and/or antibodies to hepatitis B surface antigen [anti-HBs]) must

be screened using real-time polymerase chain reaction (PCR) measurement of hepatitis B virus (HBV) DNA levels. Those who are PCR positive will be excluded. EXCEPTION: Subjects with serologic findings suggestive of HBV vaccination (anti-HBs positivity as the only serologic marker) AND a known history of prior HBV vaccination, do not need to be tested for HBV DNA by PCR.

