11. Known or suspected of not being able to comply with the study protocol (eg, because of alcoholism, drug dependency, or psychological disorder) or the subject has any condition for which, in the opinion of the investigator, participation would not be in the best interest of the subject (eg, compromise their well-being) or that could prevent, limit, or confound the protocol-specified assessments.

12. Contraindications to the use of daratumumab, azacitidine or dexamethasone per local prescribing information

13. Taken any disallowed therapies as noted in Section 6, Pre-study and Concomitant Therapy before the planned first dose of study drug

14. Received any therapy to treat cancer (including radiation, chemotherapy, biologics, cellular therapies, and/or steroids at doses > 20 mg) or undergone a major surgical procedure within 14 days, or within 5 half-lives of

an anticancer drug, prior to the first dose of study treatment, whichever is longer (with the exception of palliative radiotherapy for symptomatic management but not on measurable extramedullary plasmacytoma).

15. Participated in an interventional clinical trial(s) and received an investigational drug (including investigational vaccines) or used an invasive investigational medical device within 4 weeks before Cycle 1, Day -7 or 5 pharmacokinetic half-lives, whichever is longer

16. Had major surgery within 2 weeks before Cycle 1, Day -7, or will not have fully recovered from surgery, or has surgery planned during the time the subject is expected to participate in the study or within 2 weeks after the last dose of study drug administration.

Note: Subjects with planned surgical procedures to be conducted under local anesthesia may participate. Kyphoplasty is not considered a major surgery

NOTE: Investigators should ensure that all study enrollment criteria have been met at screening. If a subject's clinical status changes (including any available laboratory results or receipt of additional medical records) after screening but before Cycle 1 Day -7 (first dose of azacitidine) such that he or she no longer meets all eligibility criteria, then the subject should be excluded from participation in the study.

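### The 6-month washout meant to let CD38 recover names daratumumab only, so a patient given another anti-CD38 antibody between 5 half-lives and 6 months earlier passes every fixed entry criterion

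*Combined protocol and SAP*

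**What the plan says.** The purpose of the washout is given twice. The protocol abstract (study population) asks for prior daratumumab, "with most recent daratumumab treatment being at least 6 months prior to enrollment to allow for CD38 normalization". Section 3.1 says the interval makes the azacitidine-related change in CD38 measurable and will "eliminate the confounding factor of daratumumab's effect on CD38 expression".

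The operative rules are in Section 3.2: Inclusion 4, "Prior exposure to daratumumab, with most recent dose being at least 6 months prior to trial enrollment", and Exclusion 2, "Received daratumumab therapy less than 6 months prior to trial enrollment". Both name one drug.

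Other anti-CD38 antibodies are within the protocol's view. Section 1.1 cites a cohort with "disease refractory to CD38 monoclonal antibodies (MoABs), either daratumumab or isatuximab". Sections 1.2 and 8.1 treat isatuximab as a same-class antibody of comparable efficacy, and Section 8.1 takes the 8% null ORR from a trial that gave it after daratumumab. Inclusion 3 counts monoclonal antibodies among the qualifying prior therapies.

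These rules bear on prior isatuximab:
- Exclusion 14 bars cancer therapy "within 14 days, or within 5 half-lives of" the drug, whichever is longer, counted back from the first study treatment.
- Exclusion 15 sets 4 weeks or 5 half-lives if the drug was investigational.
- Exclusion 11 lets the investigator exclude a patient whose condition could confound assessments. It names no drug and no interval.
- Exclusion 13 points to a Section 6 heading on pre-study therapy that the protocol does not contain.
- Section 5.9 bars CD38-targeting drugs, but only alongside study treatment.

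The starting point of the six months also varies. Section 3.1 reads "Patients will need a washout period of at least 6 months from their most recent exposure to daratumumab prior to first dose of daratumumab", meaning the first such dose given as study treatment. The abstract, Inclusion 4 and Exclusion 2 count from enrolment.

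**The concern.** The rule is narrower than the reason given for it. If six months off an anti-CD38 antibody is needed before baseline CD38 can be trusted, that reasoning does not obviously stop at daratumumab.

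The CD38 endpoint compares two marrows in the same patient, before and after the first azacitidine course, with no control arm. Section 1.3 reports that surface CD38 falls quickly under daratumumab and later comes back. If another anti-CD38 antibody behaves the same way, some of the rise between the two marrows could be recovery from that antibody, and the analysis would credit it to azacitidine. Three secondary analyses would be exposed: the mean change, the count of patients with at least a 1.5-fold rise, and the correlation of CD38 change with response.

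**Working it through.** **1. The plan's own figures.** Section 8.1 gives 13 then 10 patients, stopping at 1 or fewer responses in 13 and rejecting at 5 or more in 23. P(reject | p) is the sum over x = 2 to 13 of P(X1 = x) × P(X2 ≥ 5 − x), with X1 ~ Bin(13, p) and X2 ~ Bin(10, p).
- p = 0.33: 0.903 (plan: 90%).
- p = 0.08: 0.030 (plan: 5% one-sided). The chance of stopping at stage 1 is 0.721.

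For the CD38 t-test (Section 8.2), the standardised effect is (1.965 − 1)/0.299 = 3.23. Power is already 0.99998 at n = 6, so the stated >99% at n = 23 holds.

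**2. Length of the gap.** No isatuximab half-life is given. As a declared proxy, Section 1.2 gives daratumumab 18 ± 9 days alone and 23 ± 12 days in combination. Six months is taken as 183 days.

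| Proxy half-life (days) | 5 half-lives (days) | Short of 183 days by |
|---|---|---|
| 18 | 90 | 93 |
| 23 | 115 | 68 |
| 9 to 27 (18 ± 9) | 45 to 135 | 138 to 48 |
| 11 to 35 (23 ± 12) | 55 to 175 | 128 to 8 |

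A gap exists for any half-life below 183/5 = 36.6 days, which covers the whole proxy range.

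**3. Timing of the baseline marrow.** Exclusion 14 counts back from the first azacitidine dose (Day −7), and the baseline marrow may be up to 14 days before that. On the central proxy values, baseline CD38 could be measured 90 − 14 = 76 to 115 − 14 = 101 days after the other antibody. The second marrow is on or before Day 1, so the two are at most about 14 + 7 = 21 days apart.

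**4. CD38 analyses (illustration only).** Suppose recovery alone adds 0.5 to the fold change, just enough to reach the 1.5-fold threshold, in k of 23 patients. The mean shifts by 0.5k/23, which is 0.022, 0.043 and 0.065 for k = 1, 2 and 3. The 1.5-fold count can rise by at most k, and each patient is 1/23 = 4.3 percentage points. The documents support no value for k or for the amount of recovery.

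**5. ORR (illustration only).** Suppose k patients respond at 8% instead of 33%, and the averaged rate is used for all 23. The rate is (22 × 0.33 + 0.08)/23 = 0.319 for k = 1, 0.308 for k = 2 and 0.297 for k = 3. Power falls from 0.903 to about 0.88, 0.86 and 0.84.

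**6. Anchor.** Counting six months to the first on-trial daratumumab dose allows the baseline marrow to fall about 21 days inside the washout, even for daratumumab. Counting to enrolment is stricter, but a screening marrow taken before enrolment could still fall up to about two weeks short.

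**The case against.** The case against has several sound parts.

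- A reader might infer that a patient treated with isatuximab about three months earlier is eligible. That needs a half-life of about 91/5 = 18.2 days or less. At 23 days the limit is 115 days and the patient is excluded. The documents support only the interval between 5 half-lives and 6 months.
- Section 3.1 speaks of daratumumab's effect on CD38, not of prior antibodies in general. No section says that isatuximab lowers CD38, by how much or for how long. Similar efficacy is not similar CD38 behaviour, so the extension is a class inference.
- The comparison is within patient over at most about three weeks. How much recovery falls in that window, months after the last antibody dose, is unknown.
- A reader might infer that ORR and the go/no-go decision are confounded. The documents tie the washout to CD38 and its endpoint, not to ORR. The effect inferred from the stated link between CD38 and response would lower response, so it would cost power and would not inflate false positives.
- Frequency is unknown. The patient needs daratumumab more than six months ago, then another anti-CD38 antibody that ended inside the gap. Exclusion 11 could also catch some of these patients.

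All of this limits the size of the point. None of it supplies a fixed rule that closes the gap. High t-test power does not help either, because power does not correct a systematic shift in an uncontrolled before/after comparison.

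**Conclusion.** The point holds as a mismatch between the washout's stated purpose and its scope. As written, the criteria can admit a patient whom the CD38 rationale would suggest keeping out, provided the other antibody's half-life is below about 36.6 days. The possible harm is an upward bias in the CD38 change and the 1.5-fold count, and distortion of the CD38-response correlation. It rests on two assumptions that the documents do not establish: that isatuximab's half-life resembles daratumumab's, and that it lowers CD38 reversibly in the same way.

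The number affected and the size of any bias cannot be derived, and confounding of ORR is not shown. No sample size, boundary, alpha or power figure is wrong because of this. The differing anchor dates are a smaller, separate inconsistency that needs settling in any case.

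**What to change.** Reconcile the abstract, Section 3.1, Inclusion 4, Exclusion 2 and Exclusion 14 with the stated rationale:

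- Extend the protocol's existing washout criterion to any anti-CD38 antibody, or state why it is limited to daratumumab.
- Use one anchor date throughout, chosen so that the baseline marrow falls outside the washout.
- Record on the CRF the date of the last anti-CD38 antibody of any kind, so that CD38 results can be read against time since that treatment.

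The cost is matching edits in a few places, one CRF field and a slightly smaller eligible pool. N = 23, the boundaries (1 of 13, 5 of 23), alpha and power stay as they are.

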3.3 Inclusion and Recruitment of Women and Minorities

Individuals of any sex/gender, race, or ethnicity may participate.

The study recruitment strategy aims to achieve representation of minority groups that reflects the demographics of the affected population in the catchment area.

3.4 Duration of Treatment

In the absence of treatment delays due to adverse events, treatment may continue indefinitely or until:

- Disease progression which requires discontinuation of the study treatment;
- Inter-current illness that prevents further administration of treatment;
- Unacceptable adverse event(s);
- Participant decides to withdraw from the study;
- Significant participant non-compliance with protocol;
- If the participant meets an exclusion criterion (either newly developed or not previously; or, recognized) that precludes further study participation
- General or specific changes in the participant's condition render the participant unacceptable for further treatment in the judgment of the investigator.

3.5 Duration of Follow Up

Each subject will be followed until 1 year after his/her last dose of study treatment, until death or withdrawal of consent for study participation, whichever occurs first. The end of study is defined as when all subjects have completed either at least 1 year of follow-up, or until death or withdrawal of consent for study participation, whichever occurs first. Further details regarding the long-term follow-up phase are detailed in [Section 6.3.3](#).

3.6 Primary Completion

The estimated primary completion is 18 months after the study opens to accrual.

3.7 Study Completion

The expected study completion date is 30 months after the study opens to accrual.

4 Investigational Products

4.1 Description, Supply and Storage of Investigational Products

Daratumumab

Classification

Anti-CD38 Antibody

Mechanism of Action

Daratumumab is an IgG1κ human monoclonal antibody directed against CD38. CD38 is a cell surface glycoprotein which is highly expressed on myeloma cells, yet is expressed at low levels on normal lymphoid and myeloid cells (Lokhorst 2015). By binding to CD38, daratumumab inhibits the growth of CD38 expressing tumor cells by inducing apoptosis directly through Fc mediated cross linking as well as by immune-mediated tumor cell lysis through complement dependent cytotoxicity, antibody dependent cell mediated cytotoxicity, and antibody dependent cellular phagocytosis.

Metabolism

None known

Contraindications

History of severe hypersensitivity (eg, anaphylactic reactions) to daratumumab or any component of the formulation.

Formulation, Appearance, Packaging, and Labeling

Daratumumab and hyaluronidase-fihj, daratumumab-SC will be provided as a fixed-dose (1800 mg), combination drug product containing rHuPH20 drug substance (2000 U/mL) and daratumumab drug substance (120 mg/mL) in a single vial. The daratumumab supplied for this study is a colorless to yellow liquid and sterile concentrate of 120 mg/mL as a liquid vial. It will be manufactured and provided under the responsibility of the sponsor. Refer to the Investigator's Brochure for a list of excipients.

Packaging

Daratumumab is supplied as glass vials containing daratumumab at a concentration of 120 mg/mL for subcutaneous administration.

Labeling

Study drug labels will contain information to meet the applicable regulatory requirements. Each vial will contain a study-specific label with a unique identification number.

Availability

Daratumumab is being obtained as study supply provided by Janssen.

Storage and handling

Daratumumab is stored at the original carton in a refrigerator at controlled temperatures ranging from 2°C to 8°C. Daratumumab must not be utilized after the expiry date printed on the label. The daratumumab product must be protected from light and must not be frozen. Daratumumab does not contain preservatives; therefore, any unused portion remaining in the vial must be discarded.

Refer to the study site investigational product and procedures manual for additional guidance on-study drug preparation, handling, and storage.

Side Effects

Complete and updated adverse event information is available in the Investigational Drug Brochure (IB) and/or product package insert.

Azacitidine**Classification**

Hypomethylating agent

Mechanism of Action

Antineoplastic effects may be a result of azacitidine's ability to promote hypomethylation of DNA, restoring normal gene differentiation and proliferation. Azacitidine also exerts direct toxicity to abnormal hematopoietic cells in the bone marrow.

Metabolism

None known

Contraindications

Hypersensitivity to azacitidine, mannitol, or any component of the formulation; advanced malignant hepatic tumors

Formulation, Appearance, Packaging, and Labeling

Azacitidine for injection is supplied as a lyophilized powder in 100 mg single-dose vials packaged in cartons of 1 vial (NDC 0591-2897-49).

Availability

Azacitidine is being obtained as commercial supply

Storage and handling

Azacitidine is stored at unreconstituted vials at 25°C (77°) with excursions permitted to 15° to 30°C (59° to 86°F). Discard unused portion.

Please refer to the package insert [REDACTED].

Side Effects

Complete and updated adverse event information is available in the current IB and/or product package insert.

Dexamethasone

Classification

Dexamethasone is a potent steroid and direct toxin for malignant plasma cells.

Mechanism of Action

Dexamethasone is a long acting corticosteroid with minimal sodium-retaining potential. It decreases inflammation by suppression of neutrophil migration, decreased production of inflammatory mediators, and reversal of increased capillary permeability; suppresses normal immune response. Dexamethasone's mechanism of antiemetic activity is unknown.

Metabolism

Substrate of CYP3A4 (major), P-glycoprotein/ABCB1; Note: Assignment of Major/Minor substrate status based on clinically relevant drug interaction potential; Induces CYP3A4 (weak)

Contraindications

Hypersensitivity to dexamethasone or any component of the formulation; systemic fungal infections. Documentation of allergenic cross-reactivity for corticosteroids is limited. However, because of similarities in chemical structure and/or pharmacologic actions, the possibility of cross-sensitivity cannot be ruled out with certainty.

Formulation, Appearance, Packaging, and Labeling

Dexamethasone is supplied as 40 mg tablets for oral administration.

Availability

Dexamethasone is being obtained as commercial supply.

Storage and handling

Dexamethasone is stored at room/ambient temperature. Please refer to manufacturer's product information for handling and storage conditions of dexamethasone.

Side Effects

Complete and updated adverse event information is available in the current IB and/or product package insert.

